Participating subjects will receive treatment using an FDA-approved f1927 laser, currently considered a standard of care treatment for melasma and hyperpigmentation in Fitzpatrick Skin Phototypes I-VI. Subjects will undergo treatments over the entire face. Subjects' response to effects of the f1927 treatment will be quantified based on evaluation of standard and clinical photography and H2 3D Imaging System images taken pre- and post-procedure. These photos will be identifiable full-face photos, and subjects will be adequately informed and consent of such. In addition to the two standard care photographic assessments, subjects will also have photos taken using the VISIA and/or VISIA-CR (Canfield Scientific, Fairfield, NJ). A quantitative assessment of the effects of treatment will be performed using VISIA and/or VISIA-CR at 1-month and 3-months post-treatments. Additional assessment will be provided by use of the Skin Hyperpigmentation Index (<https://shi.skinimageanalysis.com/> - Inselspital, Freiburgstrasse, Switzerland) [12-15] a web-based software used to quantify hyperpigmentation. Changes in the Skin Hyperpigmentation Index over time will be used to objectively report on subjects' treatment response.

From these procedures, the improvement in diffuse pigmentary changes can be evaluated in comparison to pre-treatment assessments.

Primary Endpoints

1. Quantifying Improvement in overall facial hyperpigmentation in response to laser treatment, by measuring pigmentation at baseline and follow-up visits post-treatment using the VISIA and/or VISIA-CR
2. Changes in Skin Hyperpigmentation Index (SHI) Scores from Baseline to post-treatment visits..

Secondary Endpoints

1. Monitoring incidence, severity, and relatedness of adverse events throughout the study
2. Monitoring the efficacy of pre- and post-treatment regimens with tretinoin and hydroquinone
3. Monitor the efficacy of the pre- and post-treatments with Clobetasol and ice.

Standard of Care Treatment Device

Proprietary Name	Device Description	Regulatory Information
Sciton MOXI	Aesthetic device that utilizes a fractionated laser to initiate resurfacing for the treatment of dyspigmentation and healing of photoaged skin.	Class II 510(K) Number: N/A Regulation Number: 878.4810

Study Population, Screening, and Enrollment

Study Population

The study population in question includes patients ages 18-75 with Fitzpatrick Skin Phototypes V and VI.

Subject Enrollment

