A mild bruising may occur at the treatment area. This is usually transient and resolves in a few hours to few days.

Transient edema and/or erythema (Common)

Edema and erythema typically develop within the irradiated areas but are usually temporary and fade within 24-72 hours. There is a 90% chance of transient edema and 99% chance of erythema to occur after treatment.

Skin roughness and/or peeling (Common)

Patients can expect their treated skin to feel rough like sandpaper for a few days while the skin heals. This is transient and should resolve in a few days. This is specific to the f1927 treatment.

Pigmentary changes (Rare)

This treatment can cause undesired pigmentary changes such as hyper or hypopigmentation. Although this is usually temporary, it may be permanent on rare occasions. Sun avoidance and/or the use of total sun block (SPF 30 or higher) will help to minimize the intensity and duration of pigmentary changes.

Eye injury (Rare)

There is a risk of eye injury associated with the use of this device. This risk will be minimized by wearing protective eyewear designated for use with this device. All subjects and other personnel must use proper protective eyewear during the use of this device

Scarring (Rare)

There is a small risk of scarring. However, this is minimized by proper technique and wound care.

Post-Treatment: Clobetasol (Rare)

Clobetasol is a corticosteroid that helps reduce inflammation, redness and itching on the body. Side effects of topical Clobetasol are rare and include burning, itching, swelling, irritation, dry skin, redness, rash, acne or temporary hair loss.

Standard of Care Risks and Research Risks

Assessment: Photography

Photographs will be taken using standard close-range photography, standard 3D photography using the Vectra H2, and the VISIA and/or VISIA-CR. The subject may be uncomfortable with sitting still for an extended period of time or from turning his/her body in various positions. Subjects may be sensitive to bright and repeating flashes from the camera, which can sometimes cause headaches, eye irritation, discomfort, aftereffects such as seeing spots, and in rare cases, could stimulate a migraine headache or epileptic seizure.

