The risks of photography and imaging are the same for all three imaging modalities used: close-range clinical photography (Nikon D7200), 3D Photography (Vectra H2), and the VISIA and/or VISIA-CR. Photographs include a risk of identification, as these will be full face photos. Privacy will be protected to the greatest extent possible. Photos will only be identified by unique subject identification number that contains no personal identifying information. All photos will be stored on a password secure drive, with only access by research personnel. For research purposes, photos may be used in scientific publications.

Adverse Events

At each visit, a member of the research team will question the subject about adverse events using an open-ended question. If a potential adverse event is reported by the subject or identified during examination, directed questioning and examination will be performed when appropriate. At this time, the following will be performed:

1. Obtain a complete history of the event in question as well as conduct an examination of the subject and determine if the reported event qualifies as an Adverse Event (AE). If the event is determined to be an AE, an AE case report form and Event Follow-up (EF) visit case report form must be completed. One AE case report form should be used to track the history of an individual AE throughout the period of the study.
2. Collect an updated medical and surgical history along with recording of concomitant medications or treatments.
3. Take photographs of the subject with attention to the area in question.
4. Render treatment for the event, if any, as determined by the medical judgement of the Investigator.

Photographs will be taken to document any AEs if possible.

For the duration of the study, medical assistance will be provided to the subject for study-related problems at no expense, if in the opinion of the Investigator, the reaction was caused by MOXI treatments. Should a subject choose to seek their own medical treatment, no reimbursement will be offered.

When an AE persists at the end of the study, the Investigator will ensure a follow-up of the subject until the Investigator believes that the event is satisfactorily resolved.

Subject Safety and Data Monitoring

Research Standards and Good Clinical Practice

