The conduct of this study will follow all applicable guidelines for the protection of human subjects for research as outlined in 21 CFR 50, in accordance with the accepted standards for Good Clinical Practice (GCP), International Conference on Harmonization (ICH), and the standard practices of UT Southwestern.

Data Monitoring

For this protocol, which involves the use of a non-significant risk device, the Investigator will monitor accrual, subject experience, attrition, patterns of adverse events and/or unexpected adverse events, any protocol deviations, or violations any changes in the risk/benefit analysis.

Subjects will be asked about any adverse events throughout the study. Subjects will be asked to contact the Investigator if adverse events develop between visits. If necessary, an unscheduled visit will be arranged so that the Investigator can clinically evaluate and photograph these findings.

Procedures to Maintain Confidentiality

All study records and information will be identified by the subject number. All subject identifiers will be removed from all documents. The link between subject name and study ID number will be kept in separate password-protected files. Documents containing identifying information will be kept in locked files in the research staffs' locked office. All electronic study data will be password protected with access limited to members of the research team. No direct identifying information will be shared with any outside entities. Electronic data (electronic data entry - Case Report Forms) will be password protected.

Photographs of subject's faces will be taken at enrollment, treatment, and follow-up visits. These photographs will be identified by subject numbers. Subject confidentiality will be protected to the greatest extent possible

This study will be performed in accordance with Health Insurance Portability and Accountability Act. These guidelines will be followed specifically with regard to the privacy and confidentiality of patient care and study records. Personnel associated with Investigator's office, the U.S. Food and Drug Administration (FDA) and the governing Institutional Review Board, have the right to review the data, including photographs, collected during this study.

References

1. Kaufman, B.P., T. Aman, and A.F. Alexis, *Postinflammatory Hyperpigmentation: Epidemiology, Clinical Presentation, Pathogenesis and Treatment*. Am J Clin Dermatol, 2018. **19**(4): p. 489-503.

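### Short-lived post-laser reactions are at risk of under-recording: routine adverse event questioning is open-ended and comes 20-40 days after each session

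*Combined protocol and SAP*

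**What the plan says.** The first item under Secondary Endpoints is "Monitoring incidence, severity, and relatedness of adverse events throughout the study".

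The Adverse Events section gives the routine method: "At each visit, a member of the research team will question the subject about adverse events using an open-ended question". More specific questions are conditional: "If a potential adverse event is reported by the subject or identified during examination, directed questioning and examination will be performed when appropriate". Staff then decide whether the event qualifies as an adverse event. The text gives no severity scale and no rule on whether expected reactions count.

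Potential Risks describes reactions that are very common and brief. On frequency: "There is a 90% chance of transient edema and 99% chance of erythema to occur after treatment". On duration: "Edema and erythema typically develop within the irradiated areas but are usually temporary and fade within 24-72 hours". On bruising: "This is usually transient and resolves in a few hours to few days". Roughness or peeling is put at a few days.

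In both Parts, the treatment-visit sections list the health-change and adverse event question among the activities done before that day's laser. They also say that a post-treatment assessment is performed, without giving its content, scale or form. The schedule marks a Safety Assessment at every visit, also without content. The skin in the treatment area is examined at the two follow-up visits. Between visits, Data Monitoring relies on the subject: "Subjects will be asked to contact the Investigator if adverse events develop between visits". An unscheduled visit is possible if needed.

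**The concern.** An incidence and severity endpoint needs a method that observes the event while it is present, or soon after. Here the most frequent reactions are expected to appear and fade within days, while the routine question comes about a month later and names no symptom. A subject who was red and swollen for two days, as told to expect, has little reason to mention it four weeks on. If it is mentioned, worst severity and duration have to be recalled and then graded on no stated scale.

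The recorded rate of transient reactions would then partly measure recall, and partly each staff member's view of whether an expected reaction is an adverse event. A low rate could not be told apart from non-collection. This matters for reading the two Parts side by side, because Part 2 applies Clobetasol and ice over the four days after each session, when short-lived reactions would occur.

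**Working it through.** The plan states no precision target or capture rate for adverse events, so there is no figure of its own to reproduce. The check is date arithmetic on the visit schedule, followed by a look at each other route of capture.

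**Inputs.** From Study Timeline and Procedures: sessions at Day 0, Day 30 (± 3) and Day 60 (± 3); first follow-up at Day 90 (± 7). The nominal days and windows are the same in both Parts. From Potential Risks: erythema and edema usually fade by 72 hours, that is 3 days.

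**Gap from each session to the next scheduled question** (earliest next visit minus latest session, to latest next visit minus earliest session):

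- Session 1: 30 − 3 = 27 to 30 + 3 = 33 days.
- Session 2: 57 − 33 = 24 to 63 − 27 = 36 days.
- Session 3: 83 − 63 = 20 to 97 − 57 = 40 days. If the follow-up text (1 month ± 7 days after treatment) governs instead: 30 − 7 = 23 to 30 + 7 = 37 days.

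**Margin beyond the stated resolution time.** Shortest: 20 − 3 = 17 days. Nominal: 30 − 3 = 27 days.

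**What the other routes can see.**

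| Route | Can capture | Cannot capture systematically |
|---|---|---|
| Same-day post-treatment assessment | Reactions present before the subject leaves | Later peak, duration, resolution; content and scale are not given |
| Safety Assessment row in the schedule | Not stated | No visit is scheduled in the days after a session |
| Follow-up skin examination (Day 90, Day 150) | Scarring, persistent pigmentary change | Reactions lasting hours to days |
| Subject-initiated contact | Anything the subject decides to report, including persistent swelling | Ordinary erythema, roughness or bruising that the subject regards as expected |

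**Sensitivity, for illustration only.** The documents do not say whether 99% and 90% are per subject or per session. Read per subject, 20 × 0.99 = 19.8 subjects would have erythema and 20 × 0.90 = 18.0 edema. Let c be the fraction of affected subjects whose reaction is recorded. The documents give no value, so a range of 0.25 to 1.0 is assumed:

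- Erythema recorded: 0.99 × 0.25 = about 25%, to 0.99 × 1.0 = 99%.
- Edema recorded: 0.90 × 0.25 = 22.5%, to 0.90 × 1.0 = 90%.

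The width of these ranges follows from the assumed c. They show that the recorded rate depends on a quantity that the plan neither controls nor measures; they do not estimate the loss.

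**The case against.** The strongest reply is that the open-ended question is not the whole system. There is an assessment on the day of each session, a safety assessment at every visit, two skin examinations, an open invitation to report between visits, and unscheduled visits with photographs. Directed questioning can start from an examination finding, not only from what the subject volunteers. The harms named in the primary objective, dyspigmentation and scarring, can be seen at later visits where they persist. The effect of either regimen on the acute reaction is not itself a stated endpoint, and this is a pilot of about 20 subjects.

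Most of that stands, and it limits the point. A reader might infer that nothing is collected in the first four days, or that reactions outlasting 72 hours cannot be identified. The documents support neither. The same-day assessment falls inside that window, reporting is open throughout, and persistent swelling is an explicit reason to make contact. A reader might also infer that the endpoint will be badly under-recorded, or put a count of lost episodes on it. That would need a recall rate, a per-session reading of the 99% and 90%, and a number of subjects in each Part. The documents give none of these.

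What the reply does not answer is the gap after the subject leaves the clinic. No listed route asks every subject about the same reactions, on a stated scale, close to when they occur.

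**Conclusion.** The point holds for transient reactions and their peak severity and duration, not for the whole safety endpoint. Scheduled questioning falls 20-40 days after a session across the three intervals, at least 17 days beyond the stated 72 hours, and no other route closes that gap systematically. Transient reactions are at risk of under-recording by an amount that the documents do not fix.

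This rests on two readings. One is that the open-ended question at treatment visits is the one listed before the laser. If it were also asked afterwards, it would cover only the time until the subject leaves. The other is that the same-day assessment has no structure beyond what is written. The issue is one of collection method, worth correcting because the correction is cheap.

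**What to change.** In the Adverse Events section, keep the open question and follow it at every visit with a fixed checklist of the reactions named under Potential Risks: erythema, edema, blistering, crusting, infection, bruising, roughness or peeling, hyper- and hypopigmentation, scarring, eye injury and irritation from the topical products. For each, record presence, worst severity on a stated graded scale, and start and stop dates.

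Complete the same checklist at the same-day post-treatment assessment, which gives that step a defined content. Give each subject a take-home daily symptom card for the first four days after each session, returned at the next visit. Report expected transient reactions in a solicited table, separate from other adverse events, so that the adverse event rate does not depend on an unwritten rule about expected reactions.

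Do not apply a single 72-hour cut-off to all reactions: the protocol gives that time for erythema and edema only. The prompt to make contact about swelling is more than 24 hours in the Part 2 post-treatment instructions and more than 72 hours in the treatment-visit sections of both Parts. The investigators must reconcile these passages.

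The cost is one checklist page and one card per session, with no added visit. Staff must issue, collect and enter the cards, subjects carry a small burden, and the reported reaction rate will be higher than under open questioning alone.
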